6.1.2 Disease Parameters

Measurable disease. Measurable lesions are defined as those that can be accurately measured in at least one dimension (longest diameter to be recorded) as \geq 20 mm with conventional techniques (CT, MRI, x-ray) or as \geq 10 mm with spiral CT scan. All tumor measurements must be recorded in millimeters (or decimal fractions of centimeters).

Note: Previously irradiated lesions are non-measurable except in cases of documented progression of the lesion since the completion of radiation therapy.

Non-measurable disease. All other lesions (or sites of disease), including small lesions (longest diameter <20 mm with conventional techniques or <10 mm using spiral CT scan), are considered non-measurable disease. Bone lesions, leptomeningeal disease, ascites, pleural/pericardial effusions, lymphangitis cutis/pulmonis, inflammatory breast disease, abdominal masses (not followed by CT or MRI), and cystic lesions are all non-measurable.

Note: Cystic lesions that meet the criteria for radiographically defined simple cysts should not be considered as malignant lesions (neither measurable nor non-measurable) since they are, by definition, simple cysts.

'Cystic lesions' thought to represent cystic metastases can be considered as measurable lesions, if they meet the definition of measurability described above. However, if non-cystic lesions are present in the same patient, these are preferred for selection as target lesions

Target lesions. All measurable lesions up to a maximum of 3 lesions per organ and 6 lesions in total, representative of all involved organs, should be identified as **target lesions** and recorded and measured at baseline. Target lesions should be selected on the basis of their size (lesions with the longest diameter) and their suitability for accurate repeated measurements (either by imaging techniques or clinically). A sum of the longest diameter (LD) for all target lesions will be calculated and reported as the baseline sum LD. The baseline sum LD will be used as reference by which to characterize the objective tumor response.

Non-target lesions. All other lesions (or sites of disease) including any measurable lesions over and above the 6 target lesions should be identified as **non-target lesions** and should also be recorded at baseline. Measurements of these lesions are not required, but the presence or absence of each should be noted throughout follow-up.

6.1.3 Methods for Evaluation of Measurable Disease

All measurements should be taken and recorded in metric notation using a ruler or calipers. All baseline evaluations should be performed as closely as possible to the beginning of treatment and never more than 28 days before the beginning of the treatment.

The same method of assessment and the same technique should be used to characterize each identified and reported lesion at baseline and during follow-up. Imaging-based evaluation is preferred to evaluation by clinical examination when both methods have been used to assess the antitumor effect of a treatment.

Conventional CT and MRI. These techniques should be performed with cuts of 10 mm or less in slice thickness contiguously. Spiral CT should be performed using a 5 mm contiguous reconstruction algorithm. This applies to tumors of the chest, abdomen, and pelvis. MRI is also acceptable in certain situations (e.g. for body scans). Scans will be done within 28 days prior to cycle 1 and after that every 8 weeks (+/- 7 days) until end of treatment.

Cytology, Histology. These techniques can be used to differentiate between partial responses (PR) and complete responses (CR) in rare cases (e.g., residual lesions in tumor types, such as germ cell tumors, where known residual benign tumors can remain).

The cytological confirmation of the neoplastic origin of any effusion that appears or worsens during treatment when the measurable tumor has met criteria for response or stable disease is mandatory to differentiate between response or stable disease (an effusion may be a side effect of the treatment) and progressive disease.

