4.6 Duration of Therapy

In the absence of treatment delays due to adverse events, treatment may continue until:

- Disease progression as defined radiographic progression by RECIST v1.1 criteria OR death OR symptomatic progression as clinically determined by the treating physician
- Inter-current illness that prevents further administration of treatment
- Unacceptable adverse event(s)
- Treatment held for more than 28 days
- Patient decides to withdraw from the study, OR
- General or specific changes in the patient's condition render the patient unacceptable for further treatment in the judgment of the investigator.

4.7 **Duration of Follow Up**

Patients will be followed every 3 months until death or 18 months after the last patient is enrolled, whichever occurs first. Patients removed from treatment for unacceptable adverse events will be followed until resolution or stabilization of the adverse event. Follow-up after removal from treatment is every 3 months (either clinic visit or phone call).

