4.8 Removal of Patients from Protocol Therapy

Patients will be removed from therapy when any of the criteria listed in Section 5.6 apply. Notify the Principal Investigator via email ([contact] and [contact]), and document the reason for study removal and the date the patient was removed in the Case Report Form. The patient should be followed-up per protocol.

4.9 **Patient Replacement**

Patients will not be replaced

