5.3.3 Tumor Assessments

 To be completed every 8 weeks (+/- one week) during first year of treatment and every 3 months (+/- one week) after the first year until patient comes off study

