5.4 Follow-up Procedures

Patients will be followed every three months after completion of (or early withdrawal from) study treatment until death or up to 18 months after the last patient is enrolled, whichever comes first.

• Review of systems and determination of live status (either in clinic during standard visit or by phone)

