5.5 Time and Events Table

Baseline evaluations are to be conducted within 1 week prior to administration of protocol therapy. Scans and x-rays must be done ≤4 weeks prior to the start of therapy. In the event that the patient's condition is deteriorating, laboratory evaluations should be repeated within 48 hours prior to initiation of the next cycle of therapy.

	Baseline -28 to -1 days	C1D1 +/- 3 days	At every cycle (21 days) +/- 3 days	q 8 Weeks for first year, q 3 months after the first year +/- 1 week	Off Treatment	Follow- up (q 3 months until death or up to 18 months after last patient is enrolled, whicheve r occurs first) +/- 14 days
Assessment						
Informed Consent	Χ					
History and PE	Χ	Х	X		X	
Concomitant Medications	Х	Х	Х		X	
Performance Status	Х	Х	Х		Х	
Adverse Events	X**	Х	Х		Х	
Tumor Measurements	Х			Х		
CT CAP or CT chest/MRI Abd/Pelvis	Х			Х		
CBC / CMP / UA / UPCR	Х	X	Х		Х	
PT/INR, PTT	Х	Х	X***			
TFTs (TSH, free T3, free T4)	Х	Х	X***			
CEA and CA 19-9 (optional)****			Х			
12-lead ECG	Х	Χ	X***		Х	
Pregnancy Test*	Х	Х	X***		Х	
Review of systems						Х
Study Drug Accountability			Х		Х	

^{*}Urine or serum pregnancy test is done according to local institutional standard and should be obtained ONLY in women of child-bearing potential.

^{**} Only Serious Adverse Events will be assessed and reported during baseline

^{***} To be done Day 1 of Weeks 3, 6, 9 and then every 4-6 weeks

^{****} This is an optional component and should only be collected if done according to local

institutional standards.

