5.6 Removal of Subjects from Study

Patients can be taken off the study treatment and/or study at any time at their own request, or they may be withdrawn at the discretion of the investigator for safety, behavioral or administrative reasons. The reason(s) for discontinuation will be documented and may include:

- 5.5.1 Patient voluntarily withdraws from treatment (follow-up permitted):
- 5.5.2 Patient withdraws consent (termination of treatment and follow-up);
- 5.5.3 Patient is unable to comply with protocol requirements;
- 5.5.4 Subjects who cannot tolerate the minimum protocol-specified dose of study treatment will have study treatment discontinued;
- 5.5.5 Patient demonstrates disease progression or subject no longer experiences clinical benefit as determined by the investigator (unless continued treatment with study drug is deemed appropriate at the discretion of the investigator);
- 5.5.6 Patient experiences toxicity, intercurrent illness, or specific conditions in section 4.2 that makes continuation in the protocol unsafe;
- 5.5.7 Treating physician judges continuation on the study would not be in the patient's best interest;
- 5.5.8 Patient becomes pregnant or patient is breastfeeding (pregnancy to be reported along same timelines as a serious adverse event);
- 5.5.9 Development of second malignancy (except for basal cell carcinoma or squamous cell carcinoma of the skin) that requires treatment, which would interfere with this study;
- 5.5.10 Sexually active subjects who refuse to use medically accepted barrier methods of contraception during the course of the study and for 4 months after discontinuation of study treatment
- 5.5.11 Subjects who cannot tolerate the minimum protocol-specified dose of study treatment will have study treatment discontinued
- 5.5.12 If a subject does not recover from his or her toxicities to tolerable Grade ≤ 2 within 6 weeks, the subject will have study treatment discontinued unless there is unequivocal evidence that the subject is benefitting. In this situation, a subject may be able to restart therapy with a dose reduction of the toxicity and with agreemtn of the investigator
- 5.5.13 Request by regulatory agencies for termination of treatment of an individual subject or all subjects under the protocol

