6.1.1 Definitions

Evaluable: All patients receiving cycle 1, day 1 of the protocol treatment.

Evaluable for toxicity. All patients will be evaluable for toxicity from the time of their first treatment with study drug.

Evaluable for objective response. Only those patients who have measurable disease present at baseline, have received at least one cycle of therapy, and have had their disease re-evaluated will be considered evaluable for response. These patients will have their response classified according to the definitions stated below. (Note: Patients who exhibit objective disease progression prior to the end of cycle 1 will also be considered evaluable.)

Evaluable Non-Target Disease Response. Patients who have lesions present at baseline that are evaluable but do not meet the definitions of measurable disease, have received at least one cycle of therapy, and have had their disease re-evaluated will be considered evaluable for non-target disease. The response assessment is based on the presence, absence, or unequivocal progression of the lesions.

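### The PFS-6 analysis can fall before recently enrolled patients reach six months, and scans after stopping treatment without progression are not clearly required, so some patients in the 19 or 27 may have no six-month status.

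*Combined protocol and SAP*

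**What the plan says.** **Timing.** Section 9.1 dates PFS-6 from the first dose. Section 9.3 sets the calculation at six months after the last enrolled patient starts treatment, or at that patient's progression if sooner.

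**Scans.** Four places bear on how long imaging continues:
- Section 6.1.3: "Scans will be done within 28 days prior to cycle 1 and after that every 8 weeks (+/- 7 days) until end of treatment".
- Section 5.3.3, under procedures during treatment: every 8 weeks in the first year of treatment and every 3 months thereafter, "until patient comes off study".
- Section 5.5, Time and Events Table: tumor measurements and CT/MRI are marked at baseline and in the column "q 8 Weeks for first year, q 3 months after the first year +/- 1 week". Nothing is marked under Off Treatment or Follow-up.
- Section 5.4, after treatment: only "Review of systems and determination of live status (either in clinic during standard visit or by phone".

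**Leaving treatment without progression.** Section 4.6 lists adverse events, intercurrent illness and "Treatment held for more than 28 days" among the reasons to stop. Section 5.6 separates leaving treatment from leaving the study: "Patients can be taken off the study treatment and/or study at any time at their own request".

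**Denominator and rule.** Section 6.1.1 defines evaluable as "All patients receiving cycle 1, day 1 of the protocol treatment", and section 4.9 adds "Patients will not be replaced". Section 9.2 requires at least 2 of 19 progression-free at six months, then at least 4 of 27. Section 6.1.6 counts death, radiographic progression and investigator-judged clinical deterioration as progression. No section says how to count a treated patient who is alive, without recorded progression, and without a six-month assessment.

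**The concern.** The primary endpoint is a count of patients, each needing a yes or no at six months. The plan can leave that answer missing in two ways.

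First, the date in section 9.3 depends on one patient's outcome. If the last patient progresses at the first scan, the calculation falls due while others who started shortly before are still progression-free but short of six months. They may be in perfectly good follow-up; the plan simply looks too soon.

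Second, if scans end with treatment, a patient who stops for toxicity or a long hold before six months has no required scan to settle the matter.

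The decisions turn on 1 versus 2 of 19 and 3 versus 4 of 27, so one or two unclassified patients can decide either. The trial is single-arm and open-label, so a counting rule chosen after the data are seen would weaken the error control that section 9 claims.

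**Working it through.** **Inputs.** Null rate 0.05 and alternative 0.20 (section 9.1); continue with at least 2 of 19, reject with at least 4 of 27, 80% power, 5% type I error, probability of declaring futility under the null at least 0.75 (section 9.2). The share with unknown status is not in the documents.

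**1. The plan's own figures.** Let X1 ~ Bin(19, p) and X2 ~ Bin(8, p).
P(reject) = P(X1=2)·P(X2≥2) + P(X1=3)·P(X2≥1) + P(X1≥4).
- p = 0.05: 0.1787×0.0572 + 0.0533×0.3366 + 0.0132 = 0.041.
- p = 0.20: 0.1540×0.4967 + 0.2182×0.8322 + 0.5449 = 0.803.
- P(X1≤1) at p = 0.05 is 0.755, against the stated 0.75.

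The design reproduces. The gap between 0.041 and 5% comes from the discreteness of the binomial.

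**2. How often the early trigger applies.** Section 6.1.6 counts death and clinical deterioration as progression. On the plan's own hypotheses, the last patient therefore meets that definition before six months with probability 1 − 0.05 = 0.95 under the null and 1 − 0.20 = 0.80 under the alternative. Early triggering is the usual case. How early, and how many others it catches, depends on accrual spacing, which is not given. As an illustration, suppose scans are counted from first dose (the anchor is not stated) and the last patient progresses at week 8. Six months is about 26 weeks, so anyone who started less than 26 − 8 = 18 weeks before the last patient has not reached six months. Any of them still progression-free cannot be classified.

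**3. The scan text side by side.** Section 6.1.3 ends scans with treatment. Section 5.3.3 ends them when the patient leaves the study, which section 5.6 treats as a different event. The table and section 5.4 require no imaging after treatment. The sections can therefore give different last-scan dates for the same patient.

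**4. Size if a patient not shown to be progression-free is not counted.** Let u be the share with unknown status, taken as independent of outcome. The counted success rate is p(1 − u).
- u = 0.05: rates 0.0475 and 0.19; type I error 0.035, power 0.767.
- u = 0.10: rates 0.045 and 0.18; type I error 0.030, power 0.726.

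These shares correspond on average to 0.05×27 = 1.35 and 0.10×27 = 2.7 patients.

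**5. One unknown patient among the first 19, counted each way.** The other 18 follow Bin(18, p).
- Counted as not progression-free: type I error 0.036, power 0.776.
- Counted as progression-free: type I error 0.136, power 0.912.

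The last line is hypothetical. It shows how far one classification can move the error rates.

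**The case against.** **The scan wording may already be adequate.** Section 5.3.3 read with section 5.6 can mean that scans continue after treatment, and the table's scan column is not tied to cycles. On that view section 6.1.3 is the outlier. Section 6.1.4.3 also asks sites to try to document objective progression after treatment has stopped. This stands in part: the conflict is one of wording, and the plan does not forbid later scans. But the request in 6.1.4.3 sits in a note on symptomatic deterioration and sets no schedule, and the table and section 5.4 still require nothing.

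**The affected group is small.** Stopping before six months, alive, without radiographic or clinical progression may be uncommon. Section 1.1 gives a median PFS of 2.0 months for pembrolizumab alone, section 4.2 lets either agent be modified independently, and clinical deterioration already counts as progression. This stands, and it limits the scan point. It does not answer the timing point, which can affect patients still on treatment and being scanned.

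**The early trigger may be harmless.** It may only mean that there is no need to wait for a last patient who has already progressed. With slow accrual, everyone else would have passed six months. That is plausible, but section 9.3 does not impose the condition.

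**Type I error.** A reader might infer that the stated 5% is under threat. The documents do not support that. All treated patients are in the denominator and the rule counts those who were progression-free, so an undocumented patient is most naturally not counted. Nothing suggests counting unknowns as successes.

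**Conclusion.** The concern holds in two limited parts. The section 9.3 trigger can bring the primary calculation forward to a date when some recently enrolled patients cannot be classified. Separately, the scan sections conflict, and on the section 6.1.3 reading an early stopper without progression has no required six-month assessment while remaining in the denominator.

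On the natural reading, the consequence is lost power: 0.803 falls to 0.767 at 5% unknown and 0.726 at 10%, with type I error no higher than 0.041. Both shares are assumed and taken as independent of outcome. The 0.136 figure only illustrates why the rule should be written down in advance; it does not describe this plan.

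Section 9.2 places stage two in a separate study, while the study summary expands the same cohort to 27. Both parts apply whether the last patient is the 19th or the 27th. This should be corrected, but it does not undermine the design.

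**What to change.** 1. In section 9.3, delete the clause that brings the calculation forward to the last patient's progression. Calculate PFS-6 once every treated patient has reached six months (or has already progressed or died) and the scan window used to establish six-month status has closed. Name that scan and the date from which scans are counted.
2. Reconcile sections 5.3.3, 5.4, 5.5 and 6.1.3 so that patients who stop treatment without progression stay on the existing 8-week schedule through the six-month assessment, unless they progress, die or withdraw consent.
3. State in section 9 that the count is over all treated patients and that a patient without documentation of being progression-free at six months counts as not progression-free. Report the six-month Kaplan-Meier estimate, from curves section 9.3 already plans, as a sensitivity analysis. The sponsor should also prespecify how new anticancer therapy before six months is handled.

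**Cost.** A protocol amendment with IRB approval, a few routine scans after early stopping, and a somewhat later analysis. If scans are counted from first dose, the week 24 window closes at week 25, before six months (about week 26), so using that scan adds no wait beyond six months. Using the week 32 scan would add about 33 − 26 = 7 weeks. Some power is lost if scans are missed, as shown above. The scan interval, sample size and cut-offs do not change.

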4.2 Toxicities and Dosing Delays/Dose Modifications

Any patient who receives treatment on this protocol will be evaluable for toxicity. Each patient will be assessed for the development of toxicity according to the Time and Events table (Section 5.5). Toxicity will be assessed according to the NCI Common Toxicity Criteria for Adverse Events (CTCAE), version 5.0. Dose adjustments should be made according to the system showing the greatest degree of toxicity.

Cabozantinib and pembrolizumab have class specific safety profiles based on their mechanism of action but may also cause AEs that overlap. For management of AEs which can be clearly attributed to cabozantinib or pembrolizumab, independent dose modification for either agent is allowed. Examples of VEGFR TKI associated AEs caused by cabozantinib are hypertension and hand-foot syndrome. Examples of immune-related AEs caused by pembrolizumab are pneumonitis and endocrinopathies. For AEs without clear attribution to either study treatment, management of toxicity should include dose modifications of both agents per the discretion of the investigator. Examples of overlapping AEs are diarrhea and transaminase increases.

Protocol #: UCI 18-124 MP 10/11//2022

Dose Modification Table

Dose Level	Agent	Dose
1 (starting dose)	Cabozantinib	40 mg
1 (starting dose)	Pembrolizumab	200 mg
-1 (50% reduction)	Cabozantinib	20 mg
-2	Cabozantinib	20 mg every other day

Toxicities:

Toxicity Dose Reductions			
NCI CTC Grade	Cabozantinib	Pembrolizumab	
Grade 0-2	No change from original starting dose	No change from original starting dose (unless described in 4.2.1)	
Intolerable grade 2 or grade 3	Hold until resolved to < Grade 1 then resume to dose level 1 or -1, depending on physician assessment	Hold until resolved to < Grade 2, then resume at dose level 1 (unless described in 4.2.1)	
Second episode of grade 3 or intolerable grade 2 first episode of grade 4 toxicity	Hold until resolved to ≤ Grade 1 then reduce to dose level one less than previous (i.e1 or -2) Discontinue permanently (unless investigator determines patient is deriving clear clinical benefit)	Discontinue permanently (unless described in 4.2.1)	
Third episode of grade 3	Remove subject from trial	Not applicable	

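### Scheduled scans end with treatment, so a patient who stops before month 6 without progression has no planned scan to settle radiographic PFS-6 status, and section 9 does not say how to count that patient

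*Combined protocol and SAP*

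**What the plan says.** **Scans.** Section 6.1.3 requires a scan before cycle 1 and "after that every 8 weeks (+/- 7 days) until end of treatment". Section 5.3.3, which sits under Procedures During Treatment, sets 8-weekly assessments in the first year of treatment and 3-monthly ones "after the first year until patient comes off study". The Time and Events table (5.5) marks imaging at baseline and in one calendar column, "q 8 Weeks for first year, q 3 months after the first year +/- 1 week". Its Off Treatment and Follow-up columns carry no imaging mark.

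**After treatment.** Section 4.7 says "Follow-up after removal from treatment is every 3 months (either clinic visit or phone call"). Section 5.4 gives the content: "Review of systems and determination of live status (either in clinic during standard visit or by phone"). A note in 6.1.4.3 asks for effort to document objective progression after discontinuation. It concerns patients reported with symptomatic deterioration and sets no schedule.

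**Stopping without progression.** Section 4.6 lists unacceptable adverse events and "Treatment held for more than 28 days". Section 5.6 separates leaving treatment from leaving the study. It includes "Patient voluntarily withdraws from treatment (follow-up permitted") as item 5.5.1 and physician judgment as 5.5.7. In the toxicity table of 4.2, the cabozantinib action for a third grade 3 episode is "Remove subject from trial".

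**Counting.** Everyone dosed on cycle 1 day 1 is evaluable (6.1.1), and nobody is replaced (4.9). Progression means death, radiographic progression or investigator-judged clinical deterioration due to disease (6.1.6); stopping treatment is not an event. The trial goes on with at least 2 of 19 progression-free at six months and rejects 5% with at least 4 of 27 (9.2). Section 9.3 says when PFS-6 is calculated. It has no rule for a patient whose six-month status is unknown.

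**The concern.** The primary endpoint is a yes/no status at a fixed time, and part of it can be seen only on a scan. Under 6.1.3 the scans stop when the drugs stop, for whatever reason. A patient who stops early, is alive and is clinically stable at month 6 can be read either as progression-free (no event recorded) or as not shown to be progression-free. The plan supports neither reading over the other. Other anticancer therapy is also permitted once study treatment has permanently ended (4.1.2.2), and the endpoint definition does not say how that counts.

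With cut-offs of 2 and 4 patients, one such classification can decide whether the trial expands or is declared positive. In an open-label, single-arm trial the choice would be made with the outcome in view.

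**Working it through.** **1. The plan's own figures.** With X1 ~ Bin(19, p) and X2 ~ Bin(8, p), P(reject) = Σ over x ≥ 2 of P(X1 = x) · P(X2 ≥ 4 − x).

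- p = 0.05: P(X1 ≤ 1) = 0.755 (plan: 0.75); type I error = 0.0414 (limit 0.05).
- p = 0.20: power = 0.8030 (plan: 80%).

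The design reproduces.

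**2. What the last scan tells.** Take six months as week 26. On-treatment scans fall at weeks 8, 16 and 24, each ± 1 week. A patient who stops between the week-16 and week-24 scans was last scanned at weeks 15–17, which is 9 to 11 weeks before week 26. Under exponential PFS with S(26) = p, P(progression-free at 26 | progression-free at 16) = p^(10/26), which is 0.316 at p = 0.05 and 0.538 at p = 0.20. Neither default is right for every such patient.

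**3. Model for the size (assumed).** The documents give no stopping rate and no share of progressions that would show clinically, so both are varied.

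- PFS time T is exponential with S(26) = p, so λ = −ln(p)/26.
- Time D to stopping for other reasons is exponential and independent of T, with P(D < 26) = d, so μ = −ln(1 − d)/26.
- Scanning is lost if D < T and D < 24.
- c is the share of later progressions (by week 26) that still show as death or clinical deterioration.

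Success handling (no recorded event counts as progression-free): p_s = p + (1 − c) · I, where I = [μ/(μ+λ)] · (1 − e^(−24(μ+λ))) − p · (1 − e^(−24μ)).

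Failure handling: p_f = p · P(D > 24) = p · (1 − d)^(24/26).

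Example, d = 0.10, p = 0.05: μ = 0.00405, λ = 0.1152, I = 0.0320 − 0.0046 = 0.0274. So p_s = 0.0569 at c = 0.75 and 0.0774 at c = 0. For power, p_f = 0.20 × 0.9^(24/26) = 0.1815.

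Putting p_s or p_f into the exact rule of step 1:

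| Stopping d | Type I, success, c = 90% | c = 75% | c = 50% | c = 0 | Type I, failure | Power, failure |
|---|---|---|---|---|---|---|
| 5% | 0.045 | 0.051 | 0.061 | 0.084 | 0.036 | 0.770 |
| 10% | 0.049 | 0.061 | 0.085 | 0.145 | 0.031 | 0.732 |
| 15% | 0.053 | 0.073 | 0.115 | 0.222 | 0.026 | 0.690 |

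The design values are 0.041 and 0.803.

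**4. How many patients.** At d = 0.10 the expected number of the 27 who stop before week 24 without progression is 0.86 (p = 0.05) to 1.32 (p = 0.20). Under p = 0.05, 0.56 of the 0.86 stop before week 8 and only 0.08 between weeks 16 and 24.

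**5. Exactly one or two patients.** Fix k of the 27 as unknown, split between stages by the hypergeometric distribution, with the rest binomial.

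- k = 1 as failure: type I error 0.037, power 0.778.
- k = 1 as certain success: 0.132 and 0.904.
- k = 2 as failures: 0.032 and 0.750.

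**The case against.** **Clinical events are still caught.** Death and investigator-judged deterioration remain PFS events after treatment stops, and most modelled stops under the null come early, which leaves longer for progression to declare itself. This stands. A reader might infer that success handling must push the type I error above 5%. It does not: with 90% of later progressions showing clinically, the error is 0.045 at 5% stopping and 0.049 at 10%. Nor is all PFS-6 information lost, only the radiographic part.

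**The 0.132 figure.** It fixes one patient as a certain success, with no chance of death or deterioration before month 6. It is an upper-end illustration, not an expected effect.

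**Section 5.3.3 might already cover this.** A reader might see a flat contradiction between 5.3.3 and 6.1.3, or take 5.3.3 as requiring off-treatment scans. The text supports neither firmly. Its end point is leaving the study, but it stands among on-treatment procedures and refers to the first year of treatment. It is ambiguous. The 6.1.4.3 note does not fill the gap either, for the reasons given above.

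**Few patients may stop.** Section 4.2 lets each agent be modified separately and gives two lower cabozantinib levels, and item 5.5.12 allows restarting in patients who benefit. This may keep the number small, but it does not classify those who do stop.

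**Kaplan–Meier would censor them.** Section 9.3 uses it for survival curves. The decision rule is a count, and censoring does not supply a count.

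**Conclusion.** The gap is real and should be closed. As 6.1.3 is written, early stoppers without progression have no scheduled scan to settle radiographic PFS-6 status, they stay in both denominators, and section 9 leaves their classification open.

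The size depends on assumptions: exponential PFS, independent stopping of 5% to 15% by week 26, and 0 to 90% of later progressions seen clinically. On that basis success handling gives a type I error from 0.045 to 0.22, and failure handling without continued scans gives power from 0.77 down to 0.69. With no such patient nothing changes. The two-stage design itself is sound and reproduces.

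**What to change.** 1. **Scans (6.1.3, 5.3.3, Time and Events table).** Continue the 8-weekly scans from first dose whatever the treatment status, until progression, death, withdrawal of consent to follow-up or start of new anticancer therapy. For patients off treatment the last required scan is week 24. The schedule for patients on treatment is unchanged. In the third-episode row of 4.2, state that removal is from treatment and that scans and follow-up continue.

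2. **Counting (9.3).** State one default. A treated patient who lacks a documented progression-free assessment at week 24 (± 1 week), or who is known to have died or progressed by six months, counts as not progression-free in both the 19 and the 27. Report how many were so counted, by reason. A patient who starts new therapy before week 24 will usually lack the scan and fall under this default, so add a sensitivity count for patients who started new therapy.

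**Cost.** Amendment wording, and at most three scans (weeks 8, 16, 24) of the kind already scheduled for each early stopper. N and the 2/19 and 4/27 thresholds do not change. Patients who still lack the scan cost some power: 0.778 with one and 0.750 with two, against 0.803. The type I error stays at or below its design value.
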